#### **(4) case selection**

##### 1. Inclusion criteria:

(1) diagnosis of septic shock in accordance with the Surviving Sepsis Campaign International; (2) receipt of initial fluid resuscitation in the emergency department with a hospital stay of at least 6 hours; (3) age  $\geq 18$  years; (4) provision of informed consent.

##### 2. Excluded criteria:

(1) contraindications to rapid fluid administration (e.g., end-stage renal disease, end-stage heart failure, acute pulmonary edema); (2) inability to comply with treatment, such as patients with severe trauma, burns, cancer undergoing chemotherapy, pregnant or lactating women, and those with mental illness; (3) withdrawal from treatment or transfer to another facility within 24 hours of admission.

##### 3. Elimination criteria

Subjects who have been enrolled in the study but meet one of the following criteria should be excluded:

(1) After inclusion, those who did not meet the inclusion criteria or met the exclusion criteria were found.

(2) Those who have not used test drugs / interventions.

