## **(3) Research Design Types, Principles, and Test Procedures**

### **1. Research Design**

Subjects were recruited from patients with septic shock admitted to the Emergency Department of Guangzhou Panyu District Central Hospital between July 2023 to July 2025. Demographic data of patients, including gender, age, and underlying diseases, were collected, along with mean arterial pressure, baseline lactate levels, and vital signs at enrollment. Records were made of the total fluid volume administered within the first 6 hours after patients were randomized into groups, the achievement of resuscitation targets,

blood lactate levels, blood pressure, and the incidence of complications such as pulmonary edema and renal injury. Additionally, the use of vasoactive agents (e.g., dopamine, epinephrine/norepinephrine), mechanical ventilation support, and antibiotics was documented. Patients were followed up to record the duration of emergency department stay, total hospital stay, 28-day mortality, and adverse events occurring during the study period (e.g., severe arrhythmias, anaphylactic shock).

After patients met the inclusion criteria and signed the informed consent form, random numbers were generated using SPSS 26.0 statistical software to randomly assign 73 participants to the critical care ultrasound group and the non-invasive cardiac output group. The generated random allocation table was prepared in duplicate, which were sealed and stored by the statistician and research coordinator respectively to prevent premature disclosure of group allocation information.

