In the critical care ultrasound group, patients underwent immediate bedside assessment using a Philips EPIQ 5 color Doppler ultrasound system equipped with both phased-array (1.5-4.0 MHz) and convex-array (2.0-5.0 MHz) transducers. The initial ultrasound evaluation was completed within 10 minutes of enrollment and included comprehensive hemodynamic monitoring: inferior vena cava diameter (IVC) and collapsibility index (IVC-CI) for volume status assessment, left ventricular ejection fraction (LVEF) and end-diastolic volume (LVEDV) for cardiac function evaluation, ventricular wall motion analysis, along with pulmonary B-line quantification to assess pulmonary edema. This protocol ensured real-time, comprehensive evaluation of both cardiac function and fluid status to guide resuscitation. Ultrasound reassessment was performed every 1-2 hours to dynamically adjust both the volume and rate of fluid administration until predefined resuscitation targets were achieved.

In the noninvasive cardiac output monitoring group, continuous hemodynamic assessment was performed using the NICOM system based on thoracic bioreactance technology. Following the manufacturers standard operating procedures, four electrode pads were placed at bilateral subclavicular areas and the left subcostal region. Monitoring commenced immediately after

enrollment, with baseline parameters recorded after signal stabilization ( $\leq 5$  minutes), including cardiac output (CO), stroke volume (SV), stroke volume variation (SVV), and systemic vascular resistance (SVR). The system automatically updated these parameters every 30 seconds and displayed them in real-time on the monitor screen. Fluid resuscitation was dynamically adjusted according to these continuous measurements until achieving the predefined therapeutic targets.

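### Randomised patients can be removed because of withdrawal or transfer after randomisation, while ITT is planned only as a sensitivity analysis

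*Protocol*

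**What the plan says.** Section (3), Research Design, sets the time of randomisation: "After patients met the inclusion criteria and signed the informed consent form, random numbers were generated". The assigned strategy follows at once. In the ultrasound arm, "The initial ultrasound evaluation was completed within 10 minutes of enrollment". In the other arm, monitoring begins on enrolment. Section (6), item 2, counts the fluid outcome over the 6 hours after randomisation.

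Section (4), item 2, gives as exclusion (3) "withdrawal from treatment or transfer to another facility within 24 hours of admission". Section (4), item 3, then states: "Subjects who have been enrolled in the study but meet one of the following criteria should be excluded". The two grounds are:

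- Ground (1), on eligibility, reads "After inclusion, those who did not meet the inclusion criteria or met the exclusion criteria were found".
- Ground (2) covers patients who did not receive the assigned intervention.

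The text does not say whether such patients leave the study, the main analysis or only the PP set.

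Section (10), repeated in the synopsis, names PP and ITT together as sensitivity analyses and names no main analysis set. Sections (7) and (10) make 28-day mortality the primary outcome. The synopsis instead lists lengths of stay as the main efficacy indicators and mortality as a safety index.

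**The concern.** An exclusion criterion should be decidable before allocation. This one describes something that happens to the patient during the first day in hospital, and elimination ground (1) turns it into a reason to remove a patient who is already randomised and already managed under the assigned monitor. Ground (2), not having received the intervention, is also a post-randomisation event.

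Patients in septic shock who withdraw from treatment or are transferred early may well differ in prognosis from those who stay. If they are dropped, the mortality comparison no longer covers the groups that randomisation made comparable. Even if removal is equal in both arms, the reported mortality no longer describes the randomised population. If removal differs by arm, the comparison itself is biased. The staff running the assigned monitor know the arm, so arm-related removal cannot be ruled out, although nothing in the protocol shows that it occurs.

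**Working it through.** **Order of events.**

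1. Eligibility and consent, then randomisation (section (3)).
2. Assigned monitoring starts at once, or the first scan is completed within 10 minutes of enrolment (section (3)).
3. The fluid outcome runs for 6 hours from randomisation (section (6)), so randomisation lies at the start of resuscitation.
4. Exclusion (3) can be met at any time up to 24 hours after admission (section (4), item 2).
5. An enrolled patient who meets it is to be excluded (section (4), item 3).

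Step 4 therefore usually falls after steps 1 and 2. No section makes all randomised patients the main comparison.

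**Scale available in the protocol.** No rate is given for exclusion (3). The general dropout allowance is 20%, that is 0.20 × 30 = 6 per arm. Section (3) also says the plan was to "randomly assign 73 participants to the critical care ultrasound group and the non-invasive cardiac output group", against 60 elsewhere: 73 − 60 = 13, and 13/73 = 17.8%. That gap is unexplained and may have nothing to do with removals.

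**Illustration.** Inputs from the protocol: 30 per arm, log-rank test, two-sided 0.05. Mortality is assumed to be 40% in both arms, since the background section puts it above that level. Let w be the share of an arm removed and q the 28-day mortality among those removed. Both are assumptions.

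- Removal probability is w·q/0.4 for a patient who dies and w·(1 − q)/0.6 for a survivor.
- Observed mortality after removal is (0.4 − w·q)/(1 − w).
- For w = 0.2 and q = 0.6: (0.4 − 0.12)/0.8 = 35%.
- For w = 0.2 and q = 0.8: (0.4 − 0.16)/0.8 = 30%.
- For w = 0.1: (0.4 − 0.06)/0.9 = 37.8% at q = 0.6, and (0.4 − 0.08)/0.9 = 35.6% at q = 0.8.

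With no true difference, removing 20% from one arm only thus creates an apparent difference of 40 − 35 = 5 points or 40 − 30 = 10 points. Removing 20% from one arm and 10% from the other creates 37.8 − 35 = 2.8 points or 35.6 − 30 = 5.6 points.

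Type I error was simulated with a constant hazard, censoring at day 28 and 400,000 trials per scenario (Monte Carlo standard error about 0.03 to 0.05 percentage points):

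| Removed (arm A / arm B) | q = 40% | q = 60% | q = 80% |
|---|---|---|---|
| 20% / 20% | 5.1% | 5.1% | 5.0% |
| 20% / 10% | not run | 5.4% | 6.8% |
| 10% / 0% | not run | 5.2% | 6.3% |
| 20% / 0% | 5.0% | 6.3% | 11.2% |

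Without removal the figure is 5.0%. Inflation needs two things together: unequal removal, and removed patients whose prognosis differs from the rest.

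**The 6-hour stay.** Inclusion (2) asks for "receipt of initial fluid resuscitation in the emergency department with a hospital stay of at least 6 hours". If those 6 hours run past randomisation, the same problem arises and total hospital stay is truncated from below. If they are complete or judged at screening, it does not. The text does not settle which.

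**The case against.** The strongest reply is that the elimination rule may be harmless. It does not say that patients leave the analysis. Its two grounds, an eligibility violation and an intervention not used, are typical of a per-protocol set, and section (10) plans both PP and ITT. Sections (3), (5), (6) and (12) provide for 28-day outcome without exempting removed patients. PP is also only a sensitivity analysis, so the main set is undefined rather than declared to be a reduced one, and the definition of analysis sets may properly sit in a SAP that is not shown.

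Much of this stands. The planned ITT analysis and the general 28-day follow-up are a partial safeguard, and on a PP-only reading the point shrinks to a clarification. But the protocol is not merely silent: it states a removal rule for enrolled patients and gives ITT a secondary place, and a SAP would have to override that rule.

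It is also fair that no passage supports unequal removal or high mortality among removed patients, that the 20% is a general dropout figure, and that 11.2% is an extreme case. A patient found late to have been ineligible on baseline facts is, moreover, a lesser problem than one removed for a later event. Finally, the 73-versus-60 gap and the 6-hour stay are side issues on which the conclusion does not depend.

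**Conclusion.** The concern holds and should be fixed. A post-randomisation event is written as an exclusion criterion and then used to remove enrolled patients, and no full randomised set is named as the main comparison.

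The size and direction of bias cannot be derived from the protocol. Under the stated assumptions there is no type I error inflation when removal is equal across arms or unrelated to prognosis, and modest inflation (5.4–6.8%) at 20% versus 10%. It reaches 11.2% only in the one-sided extreme. Even balanced removal can lower observed mortality from 40% to 35% or 30%. Confidence is medium, because the word used for removal is open to a PP-only reading.

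**What to change.** - State that the primary analysis includes all randomised patients by assigned arm, with day-28 vital status. First settle the conflict between the synopsis and sections (7) and (10) over which outcome is primary; the full randomised set is the right one for either.
- Say that elimination grounds (1) and (2) define only the PP sensitivity set.
- Stop using withdrawal or transfer in the first 24 hours as a ground for removal after randomisation.
- State that the 6-hour stay is judged before randomisation, or drop it.
- If recruitment is under way or complete (section (12) plans July 2023 to July 2025), apply this through the analysis set, retrieve day-28 vital status for patients already removed, subject to consent, and account for 73 against 60.

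Before recruitment the cost is wording only. Later it is a vital-status check for transferred, withdrawn or removed patients, which may be incomplete. In either case the estimate is slightly diluted relative to a per-protocol effect.

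### Eligibility eliminations after randomisation are not limited to pre-randomisation information, and the ultrasound arm's own assessment looks for an exclusion condition, so removal may be more frequent in that arm

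*Protocol*

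**What the plan says.** - Protocol, (4) case selection, 3. Elimination criteria: "Subjects who have been enrolled in the study but meet one of the following criteria should be excluded". The first criterion is "After inclusion, those who did not meet the inclusion criteria or met the exclusion criteria were found". No arm is named, and no time limit, restriction on the source of the information or arm-blind review is given.
- Protocol, (4), 2. Excluded criteria, item (1): "contraindications to rapid fluid administration (e.g., end-stage renal disease, end-stage heart failure, acute pulmonary edema".
- Protocol, (3), 1. Research Design, places randomisation after consent and then describes the two assigned assessments. For ultrasound: "The initial ultrasound evaluation was completed within 10 minutes of enrollment". It covers "left ventricular ejection fraction (LVEF) and end-diastolic volume (LVEDV) for cardiac function evaluation" and also "ventricular wall motion analysis, along with pulmonary B-line quantification to assess pulmonary edema". The NICOM baseline is listed as "including cardiac output (CO), stroke volume (SV), stroke volume variation (SVV), and systemic vascular resistance (SVR", with no lung measure.
- Protocol synopsis, efficacy evaluation, counts pulmonary edema among the complication outcomes. Section (7) names 28-day mortality as the primary outcome.
- Protocol, (8) Observation of adverse events, has clinicians weigh signs, X-ray and blood gas, without restriction to one arm.
- Protocol, (10) Statistical processing, lists per-protocol and intention-to-treat analyses as sensitivity analyses and names no main analysis set.

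**The concern.** An assigned intervention should not influence who is counted. Here one of the two interventions is, in part, a test for a listed exclusion, and the protocol orders removal of enrolled patients found to meet an exclusion. A patient who entered with unrecognised pulmonary edema has one more route to being found, within minutes, if allocated to ultrasound.

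The overlap between exclusion and outcome makes this worse. Edema seen on the first scan may be read as ineligibility, and the patient leaves. The same edema in a NICOM patient, recognised some hours later, may be counted as a complication.

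If such patients die more often than the rest, removing more of them from the ultrasound arm lowers its apparent mortality even when the two monitors perform identically. Their 6-hour fluid volume may differ too, and that is the variable on which the sample size rests. The error is systematic, so more patients would not reduce it.

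**Working it through.** The protocol gives no figure for this effect, so there is none to reproduce. The check has two parts.

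**1. Does the text allow it?**

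| Step | Ultrasound arm | NICOM arm |
|---|---|---|
| Acute pulmonary edema is an exclusion | yes | yes |
| Elimination rule applies after enrolment | yes | yes |
| Assigned assessment includes a lung measure | B-lines, first scan within 10 minutes of enrolment | none listed |
| Signs, X-ray, blood gas available | yes | yes |
| Scan or monitor findings exempt from the rule | no exemption | no exemption |

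The rule is the same in both arms. The chance of finding the condition is not.

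**2. How large could it be?**

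Inputs:
- Overall mortality M = 0.40, no true effect. Section (1) Research background puts mortality above 40%; I take 40%.
- Hidden ineligible share f = 5 to 20% of those enrolled (assumed).
- Mortality in that subgroup m = 50 to 70% (assumed).
- Proportion of the subgroup found and removed, q: 80% ultrasound v 30% NICOM (assumed), and 100% v 0% as the extreme.
- 30 patients per arm (synopsis).

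Apparent mortality in an arm after removal = (M − f·q·m) / (1 − f·q).

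Middle case, f = 0.10, m = 0.60:
- q = 0.8: (0.40 − 0.048)/0.92 = 38.3%
- q = 0.3: (0.40 − 0.018)/0.97 = 39.4%; false difference 1.1 points
- q = 1: (0.40 − 0.060)/0.90 = 37.8%; against 40.0% at q = 0, false difference 2.2 points

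Low case, f = 0.05, m = 0.50:
- q = 0.8: (0.40 − 0.020)/0.96 = 39.58%
- q = 0.3: (0.40 − 0.0075)/0.985 = 39.85%; false difference 0.3 points
- q = 1: (0.40 − 0.025)/0.95 = 39.5%; against 40.0%, false difference 0.5 points

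High case, f = 0.20, m = 0.70:
- q = 0.8: (0.40 − 0.112)/0.84 = 34.3%
- q = 0.3: (0.40 − 0.042)/0.94 = 38.1%; false difference 3.8 points
- q = 1: (0.40 − 0.140)/0.80 = 32.5%; against 40.0%, false difference 7.5 points

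With equal q in both arms the difference is 0. In the middle case with 80% v 30%, the expected removals are 30 × 0.10 × 0.8 = 2.4 patients from the ultrasound arm and 30 × 0.10 × 0.3 = 0.9 from the NICOM arm. At 30 per arm, 3.8 points is 30 × 0.038 = 1.1 deaths.

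**The case against.** Several stronger readings are tempting, and the protocol does not support them.

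- A reader might infer that fluid-intolerant patients are removed from the ultrasound arm only. The elimination rule covers both arms. Section (8) gives other routes to detection in either arm, and a low cardiac output or stroke volume on NICOM may itself point to heart failure. What remains is a likely difference in frequency.
- A reader might infer that a scan result triggers elimination. No section says so. The stated use of the scan is to adjust fluid, and no B-line or ejection-fraction threshold is tied to eligibility. But the rule as worded covers such a finding, and nothing exempts it.
- A reader might add poor cardiac function on the scan as a second route. The exclusion is end-stage heart failure, and section (1) lists myocardial depression as part of septic shock itself, so a low ejection fraction does not establish it. Pulmonary edema carries the argument.
- A reader might quote the one-sided scenario as the expected bias. It assumes complete detection in one arm and none in the other, which section (8) makes implausible.

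Three further objections have some weight. First, an intention-to-treat analysis is listed. It is only a sensitivity analysis, however, and the text does not say whether it keeps eliminated patients, so it may lessen the problem without curing it. Set definitions may sit in a SAP that is not at hand, but the removal rule is fixed in the protocol itself. Second, how exclusions are screened before randomisation is not described; the more edema is recognised at that stage, the smaller f is. Third, the direction is likely and not certain. It depends on the removed patients having worse outcomes, repeat scans may also reveal later edema as a complication in the ultrasound arm, and withdrawal for disagreement between clinical and non-invasive findings can occur in either arm.

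**Conclusion.** The concern holds in a limited form. As written, the first elimination criterion lets allocation influence who is removed, because only one arm's assigned assessment includes a lung measure for acute pulmonary edema. Removal may be more frequent in the ultrasound arm; the documents do not show that it is confined to that arm.

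The likely consequence is bias in favour of ultrasound for 28-day mortality and pulmonary edema, with distortion of 6-hour fluid volume in a direction that the documents do not settle. Under the stated assumptions the false mortality difference is about 0.3 to 3.8 points with detection of 80% v 30%, and 0.5 to 7.5 points at the extreme of 100% v 0%. Only the 40% mortality has a basis in the protocol. The hidden share, subgroup mortality and detection rates are all assumed, so the figures show scale and are not estimates. The low end is negligible. The reason to act is that the bias is avoidable at almost no cost.

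**What to change.** 1. In (4), 3. Elimination criteria, item (1), state that eligibility is judged only on information available before randomisation in both arms, and that findings from the assigned ultrasound or NICOM assessment never lead to elimination from the analysis. The limit must be on the information. Limiting it to conditions that existed before randomisation would not help, because edema first seen on the scan may well have been present at entry.
2. In (10) Statistical processing, name all randomised patients, analysed as assigned, as the main analysis set. Report any analysis that omits ineligible patients as a sensitivity analysis.

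The second change is needed because rewording item (1) alone leaves the main set unnamed and the other elimination criterion, intervention not used, still able to remove patients.

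The cost is a few sentences in two sections, with no new procedure and no extra patients. Clinical treatment of these patients is unaffected. The downside is that a few patients who are ineligible in hindsight stay in the analysis.

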##### 4. Standard for suspension of research

(1) If the following conditions occur during the experiment: cardiac arrest, intestinal perforation, intracranial and other serious complications; (2) the need for rescue is not suitable for experimental related operators; (3) The competent physician believes that the clinical condition is not suitable for continuing the experiment; (4) If the clinical symptoms

and other auxiliary examinations are inconsistent with the relevant non-invasive examination results; ( 5 ) Someone did not agree to continue the experiment during the experiment.

#### 5 .Drop-out / exit criteria

Expulsion / withdrawal criteria: ( 1 ) the competent physician believes that the clinical condition is not suitable for the continuation of the experiment; ( 2 ) If the clinical symptoms and other auxiliary examinations are inconsistent with the relevant non-invasive examination results; ( 3 ) Someone did not agree to continue the experiment during the experiment.

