## **(2) research objective**

1. Main Objective: This study explores the value of critical care ultrasound and non-invasive cardiac output monitoring in fluid resuscitation for emergency department patients with septic shock, providing evidence for optimizing hemodynamic management of septic shock, improving patient prognosis, and guiding clinical selection of appropriate monitoring modalities.

2. Secondary purpose: This study aims to explore the value of critical care ultrasound and non-invasive cardiac output monitoring in fluid resuscitation for emergency department patients with septic shock, to inform optimized hemodynamic management, improve prognosis, and guide clinical selection of monitoring modalities.

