## **(8) Observation of adverse events**

Observation of adverse events: Clinicians should evaluate the fluid resuscitation of children at any time during the experiment. If the clinical symptoms and other auxiliary examinations ( such as heart rate, liver size, mental state, X-ray, blood gas analysis, etc. ) If they are inconsistent with the relevant non-invasive examinations, the experiment should be terminated immediately and the superior physician should be found in time to assist.

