## **(10)Statistical processing**

This study adopted a prospective randomized controlled design, and the sample size was estimated using PASS 15.0 software. Based on the difference in 6-hour fluid resuscitation volume between the two groups in the pilot study (mean difference 1261 mL, standard deviation 3155 mL),  $\alpha=0.05$  (bilateral) was set  $\beta=0.2$ , Calculated to require 27 cases per group, considering a 20% dropout rate, 60 cases were ultimately included. Use SPSS 26.0 to generate block random sequences (block size 4), and allocate concepts through sealed envelopes. The normality of the measurement data was confirmed by Shapiro Wilk test, and those that conform to the normal distribution were expressed as mean  $\pm$  standard deviation. Independent sample t-test was used for inter group comparison; non normally distributed individuals are represented by the median (interquartile range) and Mann Whitney U test is used. The categorical data is presented in terms of the number of cases (%), and the comparison between groups is conducted using the chi square test or Fishers exact test (when the theoretical frequency is less than 5). The main outcome (28 day mortality rate) was plotted using Kaplan Meier survival curve, and inter group differences were analyzed using log rank test, and HR (95% CI) was calculated. Secondary outcomes (such as fluid dosage, MAP, etc.) report mean difference (MD) or relative risk (RR) and their 95% confidence intervals. All tests are bilateral, and  $P<0.05$  is considered statistically significant. Perform Bonferroni correction on secondary outcomes ( $\alpha=0.05/6 \approx 0.008$ ). Multivariate Cox regression was used to adjust for confounding factors such as age and baseline lactate, and sensitivity analysis included protocol set (PP) and intention to treat (ITT) analyses. The statistical software used is R 4.3.1 (R Foundation) and SPSS 26.0 (IBM).

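### Patients are withdrawn when clinical findings disagree with the monitor, a post-randomisation failure of the strategy under test, and the protocol does not keep them in follow-up or in the main comparison

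*Protocol*

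**What the plan says.** **Exit.** Section (4), item 5 (Drop-out / exit criteria) lists two relevant grounds for expulsion or withdrawal, apart from refusal to continue. One is "the competent physician believes that the clinical condition is not suitable for the continuation of the experiment". The other is "If the clinical symptoms and other auxiliary examinations are inconsistent with the relevant non-invasive examination results".

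**Suspension.** Item 4 (Standard for suspension of research) repeats the disagreement trigger as its fourth condition. Its first condition names "cardiac arrest, intestinal perforation, intracranial and other serious complications".

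**Adverse events.** Section (8) returns to disagreement between the clinical picture and the monitor: "If they are inconsistent with the relevant non-invasive examinations, the experiment should be terminated immediately".

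**Elimination.** Section (4), item 3 excludes already enrolled patients who did not receive the intervention.

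**Objective.** Section (2) states: "This study explores the value of critical care ultrasound and non-invasive cardiac output monitoring in fluid resuscitation for emergency department patients with septic shock". Under section (3), fluid is adjusted on repeated ultrasound in one arm and on NICOM readings in the other.

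**Analysis.** Section (10), and the statistical row of the synopsis in the same words, say: "sensitivity analysis included protocol set (PP) and intention to treat (ITT) analyses". No main analysis population is named.

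**Follow-up.** Sections (5) and (6) list 28-day mortality among the data recorded, and section (12) foresees 28 days of follow-up. None of them says what happens to a patient who has met an exit criterion.

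**The concern.** The trial compares two ways of guiding fluid. A reading that contradicts the bedside picture is one of the ways in which such guidance fails, so it is a result of the randomised strategy and not a neutral reason for leaving the study. It is also plausibly related to prognosis.

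If patients stop contributing data at that moment, what remains is a comparison among patients in whom the monitor and the clinicians agreed. Randomisation no longer protects that comparison. The two devices measure different things, so both the number and the kind of exits may differ between arms, and the resulting bias can favour either one. With 30 patients per group, a handful of such exits could create or hide a difference in 28-day mortality. The same applies to complications, resuscitation success and length of stay.

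**Working it through.** **1. Is the trigger an outcome of the strategy?** Both assigned methods are non-invasive, so the exit criterion is naturally read as covering the monitor in either arm, although the term is not defined. The trigger can occur only once the assigned monitor has been used, which is after randomisation. Section (2) makes the value of that monitor the object of study. The event therefore belongs to what is being measured.

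**2. Does the protocol keep these patients?**

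| Place | What it settles | What it leaves open |
|---|---|---|
| (4) item 5 | Disagreement leads to withdrawal | Whether follow-up continues |
| (4) item 4 | Disagreement and serious complications lead to suspension | Whether the patient, the procedure or the study is suspended |
| (8) | Disagreement leads to immediate termination | What is terminated |
| (4) item 3 | Patients without the intervention are excluded | From which analysis |
| (5), (6), (12) | 28-day outcome is recorded | Whether this covers exited patients |
| (10) and synopsis | ITT and per-protocol are sensitivity analyses | Which population is the main one |

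No entry keeps an exited patient in follow-up or in the main comparison.

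**3. How large could the effect be?** The plan gives no exit count by reason and no mortality among exits, so there is no figure of its own to reproduce. What follows is an illustration.

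Inputs from the protocol:
- 30 patients per group (synopsis).
- Background mortality above 40% (section (1)); 40% is used, so 30 × 0.40 = 12 deaths per arm and no true difference.
- A 20% dropout allowance (section (10)), which is 30 × 0.20 = 6 patients per arm.

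Assumptions: 6 exits in one arm and 2 in the other, with mortality q among exits, and exits dropped from the analysis.

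Observed mortality = (12 − k × q) / (30 − k), where k is the number of exits.

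| q | Arm with 6 exits | Arm with 2 exits |
|---|---|---|
| 40% | (12 − 2.4)/24 = 40.0% | (12 − 0.8)/28 = 40.0% |
| 70% | (12 − 4.2)/24 = 32.5% | (12 − 1.4)/28 = 37.9% |
| 90% | (12 − 5.4)/24 = 27.5% | (12 − 1.8)/28 = 36.4% |

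The spurious difference is 0, 5.4 and 8.9 percentage points in turn. If exits occur in one arm only, 6 exits move that arm from 40% to (12 − 3.6)/24 = 35.0% at q = 60%, and to (12 − 6)/24 = 25.0% at q = 100%.

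Two conditions remove the bias in this setting: exits that die at the overall rate, or all randomised patients kept and followed to day 28. Only the second is under the sponsor's control.

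**The case against.** The strongest reply is that removal is inferred. The protocol never says that data from exited patients are discarded. Only item 3 uses the language of exclusion, sections (5), (6) and (12) record 28-day outcome without an exception for exits, and an ITT analysis is planned. The main population may be fixed in a statistical analysis plan that is not at hand. This stands in part: a reader might infer that exited patients are deleted, and the text does not say so. But exit rules and follow-up after exit are protocol matters, and an analysis plan cannot recover day-28 status that was never collected. Section (10) has also already placed ITT among the sensitivity analyses.

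Three further limits stand.
- **Cardiac arrest.** A reader might conclude that patients leave at cardiac arrest, just before the death that the trial counts. It appears only in item 4, under suspension of research, and not in the exit list of item 5. The refusal condition in item 4 points to the individual patient, but the heading leaves the question open.
- **Device frequency.** A reader might argue that NICOM, refreshed every 30 seconds, gives 6 × 3600 / 30 = 720 occasions for disagreement in 6 hours, against about 3 to 6 repeat scans at intervals of 1–2 hours. That does not follow. Automatic refreshes are not separate clinical comparisons, section (8) has clinicians evaluate at any time in both arms, and guidance runs only until targets are met. Unequal exit is possible because the devices differ, but its direction is unknown.
- **Section (8)** speaks of children, although the inclusion criteria require age 18 or over. It is weak corroboration, and the mismatch needs reconciling. Item 5 carries the point without it.

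**Conclusion.** The point holds in this form: the protocol makes disagreement with the assigned monitor a ground for withdrawal and does not secure follow-up or a place in the main comparison for the patients concerned. Followed as written, it can yield a comparison conditioned on the monitor having agreed with the clinicians. This is more than missing detail, because the exit criterion is itself an outcome of the strategy under test.

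The size cannot be derived from the documents. The figures of 32.5% against 37.9% rest on assumed exit counts and assumed mortality among exits, and the bias is zero if exits die at 40%. They show what a few exits can do in arms of 30, not what will happen.

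The documents do not support saying that exited data are deleted, that cardiac arrest removes a patient, or that NICOM will produce more exits. If the suspension rule in item 4 is meant per patient, the same problem arises close to 28-day mortality, which sections (7) and (10) treat as the main outcome. The protocol should say which is meant.

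**What to change.** Leave the clinical triggers as they are, and change only what meeting one means for the study.

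1. **Section (4) items 4 and 5, and section (8):** state that, for study purposes, meeting a trigger does not end follow-up. The patient stays in the assigned group, and 6-hour fluid volume, complications, length of stay and day-28 vital status are still collected unless consent for data is withdrawn. In item 4, say whether the patient or the study is suspended.
2. **Section (10) and the statistical row of the synopsis:** make the as-randomised (ITT) analysis the main one, with per-protocol as sensitivity.
3. **Section (4) item 3:** limit the exclusion of patients who did not receive the intervention to the per-protocol set. Otherwise it contradicts the change in step 2.
4. **Case report form:** record monitor–clinical disagreement by arm, with number and time. It bears directly on the value of each monitor.

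The cost is a few sentences, an added case-report field, and follow-up of exited patients to day 28. The downside is small: each arm will include some resuscitation not guided by its monitor, which dilutes the pure device effect. The per-protocol analysis can show that.
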